1.0 TRIAL SUMMARY

Abbreviated Title	Pembrolizumab and palliative radiotherapy in metastatic gastroesophageal cancer
Trial Phase	II
Clinical Indication	SCC and/or adenocarcinoma of the esophagus, GEJ, and stomach
Trial Type	Prospective; Biomarker analysis
Route of administration	Intravenous
Trial Blinding	None
Treatment Groups	All patients will be assigned to the same therapy of palliative radiotherapy of 30 Gy over 10 fractions for symptoms from their primary tumor or a single target metastatic site in combination with pembrolizumab at a fixed dose of 200 mg every 3 weeks.
Number of trial subjects	14
Estimated enrollment period	24 months
Estimated duration of trial	36 months from the first patient signing informed consent until the last patient's last visit.
Duration of Participation	Patients will complete radiation therapy of 30 Gy in 10 fractions and will continue pembrolizumab until confirmed disease progression, or intolerable toxicity, or an initial 35 administrations (approximately 2 years). Patients who stop pembrolizumab with stable disease or better or 35 administrations of therapy without progression may be eligible at the discretion of the investigator to receive up to an additional year of pembrolizumab therapy. Patients with evidence of progressive disease (PD) on imaging and are clinically stable may continue to be treated at the discretion of the investigator.

2.0 TRIAL DESIGN

2.1 Trial Design

This is a single-arm, prospective, phase II, biomarker analysis trial of pembrolizumab in combination with palliative radiotherapy for patients with metastatic squamous cell or adenocarcinoma of the esophagus, stomach, or gastroesophageal junction (GEJ). We will enroll 14 patients within our institution who are in need of palliative radiation for symptoms related to their primary tumor including pain, dysphagia, and bleeding. Patients with a single metastatic site in need of palliative radiation (e.g., pain from a bony metastasis, enlarged lymph nodes, liver metastasis, etc.) will also be eligible provided they have other measurable metastatic sites outside of the radiation field. The exception will be patients who require palliative radiation to a symptomatic central nervous system (CNS) metastasis. The first dose of palliative radiation and first dose of pembrolizumab will commence on cycle 1, day 1.

Participation in this trial will be dependent on patients having a metastatic site amenable to ultrasound and/or CT-guided biopsy, inclusive of patients with malignant ascites amenable to ultrasound-guided aspiration, and agreeing to provide pre- and post-treatment biopsies for the

IRB Protocol No. 16099

Version: 04

[figure not shown]
Version Date: 10/16/2019

biomarker analysis primary endpoint of the study. Patients who are undergoing palliative radiation for a single target metastatic site, and only the primary tumor is amenable to biopsy are also eligible to participate if they consent to endoscopic pre- and post-treatment biopsies.

Treatment will continue until documented clinical PD, unacceptable AE(s), intercurrent illness that prevents further administration of treatment, investigator's decision to withdraw the patient, patient withdraws consent, pregnancy of the subject, noncompliance with trial treatment or procedure requirements, completion of 35 administrations (approximately 2 years) of treatment with study medication or achievement of a complete response.

2.2 Trial Diagram

Study Schema

3.0 OBJECTIVE(S) & HYPOTHESIS(ES)

3.1 Primary Objective(s) & Hypothesis(es)

(1) **Objective:** To establish that the combination of pembrolizumab and traditional external beam multifractionated RT to the primary tumor or a single target metastatic site of patients with metastatic gastric, esophageal, and/or GEJ cancers will lead to an increase in tumor infiltrating cytotoxic T-cells and circulating cytotoxic T cells and a reduction in immunosuppressive Tregs and MDSCs in metastatic sites.

Hypothesis: The combination of pembrolizumab and traditional external beam multifractionated RT to the primary tumor or a single target metastatic site will lead to increased immune-mediated tumor cytotoxicity via a demonstrable increase in tumor infiltrating and circulating cytotoxic T cells and a reduction in immunosuppressive Tregs and MDSCs within metastatic sites post-therapy.

3.2 Secondary Objective(s) & Hypothesis(es)

(1) **Objective:** To establish that the combination of pembrolizumab and RT is feasible in this patient population and evaluate toxicities per NCI CTCAE ver.4.03.

Hypothesis: The combination of pembrolizumab and RT will be feasible with an acceptable safety profile to warrant future studies.

(2) **Objective:** To evaluate overall response rate (ORR) per RECIST1.1 and irRECIST in this treatment population and correlate with tumor T-cell response.

Hypothesis: The combination of pembrolizumab and RT will demonstrate clinical efficacy with a promising response rate compared to historical controls to warrant future studies.

(3) **Objective:** To evaluate progression-free (PFS) and overall survival (OS) in this treatment population.

Hypothesis: The combination of pembrolizumab and RT will demonstrate promising PFS and OS to warrant future studies.

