4.2 Rationale

4.2.1 Rationale for the Trial and Selected Subject Population

Metastatic squamous cell carcinomas (SCC) and adenocarcinomas of the esophagus, stomach, and gastroesophageal junction (GEJ) account for a high proportion of worldwide cancer-related mortality. While some progress has been made for HER2 and VEGFR2 targeted therapies in adenocarcinomas,^{1,2} options for metastatic SCC remain dismal. Evidence for cytotoxic agents in SCC typically stem from a small proportion of patients enrolled in large phase III trials predominated by patients with adenocarcinoma histologies.³ Novel targeted therapeutic approaches for both subtypes are desperately needed.

Pembrolizumab has demonstrated encouraging preliminary evidence of activity in small cohorts of gastric and esophageal cancer patients within the KEYNOTE-012 and KEYNOTE-028 trials, respectively.^{4,5} Both trials selected for patients with evidence of PD-L1 expression within tumor stroma and/or tumor cells. KEYNOTE-012 reported a 22.2% overall response rate by central review, while KEYNOTE-028 noted a 30.4% overall response rate when assessed by investigator review. The activity of pembrolizumab in gastroesophageal cancer patients without tumor PD-L1 expression remains unknown, though lack of PD-L1 expression does not necessarily translate to an absolute lack of response to immune checkpoint inhibitors in pooled analyses of patients with melanoma, NSCLC, and genitourinary malignancies.⁶ Given the promising early evidence of clinical efficacy in gastroesophageal cancers, strategies should be further developed to enhance the potency of immune checkpoint inhibitors, even in patients whose tumors are currently not considered to have detectable PD-L1 expression.

The abscopal effect is a rarely observed though well annotated clinical phenomenon in cancer radiotherapy (RT), in which non-irradiated metastatic lesions distant from the primary tumor site directly subjected to radiation are noted to regress. This phenomenon has been attributed to immune-mediated effects in preclinical models,⁷ and provides rationale that immune checkpoint inhibition and RT could act synergistically. In a recent preclinical study, PD-1 was reported to suppress RT antitumor response, though delivery of a PD-1 blocking antibody

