We propose a prospective trial to assess pre- and post-treatment biopsies of patients' metastatic sites with the hypothesis that tumor cytotoxic T cells will be increased with combining pembrolizumab and palliative RT with corresponding improvement in clinical activity. As we will only be radiating a single target lesion in this study population, assessment of response among non-irradiated metastatic sites will serve as a true measure of the abscopal effect. Toxicities are not anticipated to be overlapping for these two modalities, though safety should still be assessed in this early cohort of patients to ensure immune-mediated or radiation-induced toxicities are not exacerbated by the combination. At City of Hope where patients will be solely recruited for this trial, we have extensive experience in the conduct of pre- and post-treatment biopsy studies having completed accrual to a pilot trial of the novel nanopharmaceutical CRLX101 in this disease subset (Clinicaltrials.gov, NCT01612546). We also have a broad gastroesophageal cancer patient population evaluating more than 60 new cases per year due to our institution serving the diverse, multicultural population of the San Gabriel Valley in Los Angeles County. [name], MD, Chair of the Department of Immuno-Oncology, will serve as a collaborating investigator on this study given his laboratory's expertise in translational analyses of tumor/immune/stromal cell interactions.

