9.0 STATISTICAL ANALYSIS PLAN

9.1 Primary Objective

The primary objective of this study is to establish that the combination of pembrolizumab and a palliative course of traditional external beam multifractionated RT in patients with metastatic gastric, esophageal, and/or GEJ cancers will lead to an increase in tumor infiltrating cytotoxic T-cells and circulating cytotoxic T cells and a reduction in immunosuppressive Tregs and MDSCs in non-irradiated sites.

Each patient will serve as their own control, and tumor cytotoxic T cell infiltration and immunosuppressive Tregs will be compared pre- and post-treatment. As variability of the difference in the T cell populations pre- and post-treatment is unknown and still being established, the power calculation is based on the concept of “effect size” in this biomarker analysis study. Specifically, a sample-size of 14 patients will have 80% power to detect an effect size of 0.71 using a paired t-test with a 0.05 one-sided significance level. The effect size is the mean difference divided by the standard deviation of the difference.

A positive biological signal combined with acceptable secondary endpoints (response and toxicity) are sought for a clear indication of promise of this combination.

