9.2 Secondary Objectives

Secondary objectives such as ORR per RECIST 1.1 and irRECIST, PFS, and OS are exploratory, though will also be documented, along with toxicity. All patients who receive at least one dose of pembrolizumab will be included in the safety analysis. Stool/oral microbiomic profiling and germline miRNA biomarker panel analyses will also be correlated with secondary outcome measures of ORR and toxicities.

While overlapping toxicities are not anticipated with the combination of pembrolizumab and RT, the initial treatment of patients within this trial warrants a careful review of toxicity:

- **Toxicity-based Interim Analysis:** A study hold will be placed for re-evaluation at the proposed starting dose as accrual proceeds on this phase II study according to the following rule: The study will hold pending an amendment if 3 patients discontinue therapy after cycle 1 due to treatment-related toxicity. This rule has a 97% chance of holding the study if the true discontinuation rate due to toxicity on cycle 1 is 50%. It has a 15% chance of holding if the true discontinuation rate on cycle 1 is 15%.
- **Treatment-related mortality stopping rule:** Any treatment-related death will hold the study accrual pending review by the PI, Sponsor, and DSMB/IRB.

With 14 patients, there is 96% power to detect at least one responder if the true response rate is 21% or higher, which is in the range of 22% in the phase I trial of pembrolizumab among gastric cancer patients with PD-L1 overexpression. As a result, failure to observe any response in the 14 patients would result in lack of enthusiasm for the combination of pembrolizumab and RT in this patient population. PFS and OS will be determined using the Kaplan-Meier method.

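### The T-cell correlation names only ORR, with about three responders expected in 14 patients; percentage change in non-irradiated target lesions would keep roughly twice the information

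*Combined protocol and SAP*

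**What the plan says.** Objective (2) in section 3.2 is "To evaluate overall response rate (ORR) per RECIST1.1 and irRECIST in this treatment population and correlate with tumor T-cell response". The rationale in section 4.2.1 hypothesises that "tumor cytotoxic T cells will be increased with combining pembrolizumab and palliative RT with corresponding improvement in clinical activity".

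Section 9.2 calls ORR, PFS and OS exploratory. It gives no test, significance level or sidedness for the T-cell correlation. On response it says "With 14 patients, there is 96% power to detect at least one responder if the true response rate is 21% or higher". It also says that the microbiome and germline miRNA analyses "will also be correlated with secondary outcome measures of ORR and toxicities". Exploratory objective 3.3(2) adds PFS and OS for the microbiome.

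Percentage change in tumour size is not named as an endpoint or correlate. The measurements behind it are nevertheless required. Inclusion criterion 7 (section 5.1.1) asks for RECIST-measurable disease outside the irradiated lesion, section 7.1.2.6.1 asks for at least one target lesion at baseline, and section 7.1.2.6.2 schedules scans every 6 weeks through cycle 6 and every 9 weeks after that.

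**The concern.** For one patient, ORR is responder or non-responder. With about three responders expected, the planned link between immune change and clinical effect compares roughly three patients with eleven. With no responders it cannot be estimated, and with one it rests on a single patient.

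This matters because objective 3.2(2) is the only stated analysis that ties tumour T-cell change to a clinical outcome within patients. A yes/no outcome discards the degree of shrinkage or growth, which RECIST measurement already supplies. In a trial this small, that is a large share of what can be learned about the link.

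**Working it through.** **Inputs from the documents.** n = 14 (section 2.1: "We will enroll 14 patients within our institution"). Response rate 21% (section 9.2). Reference rates in section 4.2.1: "KEYNOTE-012 reported a 22.2% overall response rate by central review" for gastric cancer, and 30.4% for oesophageal cancer in KEYNOTE-028. The design level is one-sided 0.05, borrowed from the primary test in section 9.1 ("80% power to detect an effect size of 0.71 using a paired t-test with a 0.05 one-sided significance level") because none is given for the correlation.

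**Assumptions, not in the documents.** Bivariate normal T-cell change and tumour change; true correlation 0.3 to 0.8; responders are the patients with the most shrinkage.

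**1. The plan's own figures reproduce.** P(at least one responder) = 1 − 0.79^14 = 1 − 0.037 = 0.963, against 96% stated. The paired t-test with n = 14, effect size 0.71 and one-sided 0.05 has power 0.808 by the noncentral t, against 80% stated.

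**2. Responder count.** Expected: 14 × 0.21 = 2.94. P(0) = 0.037. P(1) = 14 × 0.21 × 0.79^13 = 0.137. P(0 or 1) = 0.174. At 22.2% the expected count is 3.1; at 30.4% it is 4.3.

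**3. Information kept by a yes/no cut.** Relative efficiency = φ(z)² / [p(1 − p)], where z is the normal cut-point. At p = 0.21, φ(z) = 0.288, so 0.0831 / 0.1659 = 0.50. At 22.2% it is 0.51; at 30.4% it is 0.58.

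**4. Power by simulation** (40,000 runs per row, n = 14, 21% response, one-sided 0.05):

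| True correlation | Pearson | Yes/no, point-biserial | Spearman | Yes/no, exact rank-sum |
|---|---|---|---|---|
| 0.3 | 0.28 | 0.18 | 0.26 | 0.14 |
| 0.4 | 0.43 | 0.25 | 0.38 | 0.20 |
| 0.5 | 0.60 | 0.35 | 0.54 | 0.28 |
| 0.6 | 0.78 | 0.46 | 0.71 | 0.38 |
| 0.7 | 0.92 | 0.59 | 0.86 | 0.50 |
| 0.8 | 0.98 | 0.72 | 0.96 | 0.64 |

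For correlations 0.4 to 0.7 the relative loss is 36-42% for the parametric pair and 42-48% for the rank pair. Part of the rank-pair gap is conservatism: the exact rank-sum test rejects 3.4% under the null. With exactly three responders its null rate is 4.5%, and its power at correlation 0.6 is 0.41.

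**5. Sensitivity at correlation 0.6.**
- Two-sided 0.05: 0.67 falls to 0.33 (parametric), 0.58 to 0.26 (rank).
- Response rate 30.4%, one-sided: 0.78 falls to 0.53, 0.71 to 0.46. Across correlations 0.5 to 0.7 the loss is 26-37%.
- Three ordered categories (21% CR/PR, an assumed 25-45% SD, the rest PD; 20,000 runs), analysed by Spearman: 0.61-0.65, against 0.71 for the continuous outcome.
- An assumed 10 evaluable pairs: 0.62 falls to 0.34 (parametric). Fewer than 14 tissue pairs is plausible, because section 7.1.2.7.1 sends ascites to culture and expansion only and section 9 makes no dropout allowance.

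**6. Ranking rule.** Placing the second-best of 14 patients last by mistake cuts Spearman power at correlation 0.6 from 0.71 to about 0.34, below the yes/no analysis in the table. How early PD is ranked therefore matters.

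**The case against.** The strongest reply is that the plan does not commit to a yes/no analysis. It gives no method, and for the germline panel section 7.1.2.7.2 speaks of RECIST1.1 and irRECIST responses, which could mean ordered categories. On that reading most of the loss goes (0.61-0.65 against 0.71). This stands as a limit on the size. It does not remove the point: ORR is still the only clinical variable named for the T-cell correlation, and the choice should be fixed before data are seen.

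Second, the analysis is exploratory. Section 9.1 looks for a biological signal together with acceptable response and toxicity, and no decision rule depends on this correlation. That stands, and it limits the weight of the point.

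Third, low power comes partly from n = 14. At correlation 0.4 even Spearman has only 38%.

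A reader might infer two stronger claims. One is that the plan gives up close to half its power. The documents supply no correlation, distribution, test or level for this analysis, and on one-sided parametric tests the loss at 21% is nearer two-fifths. The other is that a real link is more likely missed than found. At correlation 0.7 the yes/no tests reach 50-59%.

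Fourth, percentage change ignores new lesions, and a crude correction would do harm. Table 4 allows for a repeat scan showing SD, PR or CR after a first PD, and section 7.1.2.7.2 collects blood at first progression because it may be pseudoprogression. Ranking every first PD by new lesion last would contradict that. This stands and shapes the fix.

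**Conclusion.** The point holds in a limited form. Objective 3.2(2) and section 9.2 name only ORR for the T-cell correlation and give no method, with 2.94 responders expected and a 17% chance of at most one. Those counts follow from the plan's own figures.

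The efficiency loss is conditional. If response is analysed as yes/no and the relation is bivariate normal, about half the information is kept at a 21% response rate. At an assumed correlation of 0.6 and one-sided 0.05, power is about 71-78% continuous against 38-46% yes/no. This is a worthwhile improvement to an exploratory analysis and does not affect the primary test.

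**What to change.** In sections 3.2(2) and 9.2:

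- Define the T-cell correlation as a Spearman correlation, with confidence interval, between within-patient T-cell change and best percentage change in the sum of target-lesion diameters outside the radiation field. The interval matters because power is modest at weak correlations.
- Keep the responder/non-responder comparison as descriptive.
- Give the worst (tied) rank only to patients whose best outcome is PD confirmed through the irRECIST/Table 4 process, or who die or progress clinically before an evaluable scan. A patient with an unconfirmed first PD by new lesion keeps the measured percentage change, as does one who shrinks and later progresses.
- For the microbiome, the same continuous outcome may be added to ORR, PFS and OS.
- For the germline panel, keep yes/no response, because the performance cited in section 7.1.2.7.2 is specificity for response.

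Cost: no new scan, visit or sample. The wording change is a protocol amendment and needs IRB approval under section 12.1. The remaining weakness is that percentage change does not capture new lesions except through the rank rule.

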3.3 Exploratory Objectives

(1) **Objective:** To measure changes in whole genome serum miRNA signatures before and after protocol therapy and correlate with tumor/immune/stromal cell miRNA expression profiling determined by deep sequencing.

(2) **Objective:** To measure changes in fecal and oral microbiomic diversity and correlate with ORR, PFS, and OS.

(3) **Objective:** To assess germline mutations in a panel of miRNA regulatory genes using the MiraDx assay as predictors of response and toxicity to pembrolizumab and RT.

4.0 BACKGROUND & RATIONALE

4.1 Background

Refer to the Investigator's Brochure (IB)/approved labeling for detailed background information on pembrolizumab (aka MK-3475).

4.1.1 Pharmaceutical and Therapeutic Background

The importance of intact immune surveillance in controlling outgrowth of neoplastic transformation has been known for decades. Accumulating evidence shows a correlation between tumor-infiltrating lymphocytes (TILs) in cancer tissue and favorable prognosis in various malignancies. In particular, the presence of CD8+ T-cells and the ratio of CD8+ effector T-cells / FoxP3+ regulatory T-cells seems to correlate with improved prognosis and long-term survival in many solid tumors.

The PD-1 receptor-ligand interaction is a major pathway hijacked by tumors to suppress immune control. The normal function of PD-1, expressed on the cell surface of activated T-cells under healthy conditions, is to down-modulate unwanted or excessive immune responses, including autoimmune reactions. PD-1 (encoded by the gene *Pdcd1*) is an Ig superfamily member related to CD28 and CTLA-4 which has been shown to negatively regulate antigen receptor signaling upon engagement of its ligands (PD-L1 and/or PD-L2). The structure of murine PD-1 has been resolved. PD-1 and family members are type I transmembrane glycoproteins containing an Ig Variable-type (V-type) domain responsible for ligand binding and a cytoplasmic tail which is responsible for the binding of signaling molecules. The cytoplasmic tail of PD-1 contains 2 tyrosine-based signaling motifs, an immunoreceptor tyrosine-based inhibition motif (ITIM) and an immunoreceptor tyrosine-based switch motif (ITSM). Following T-cell stimulation, PD-1 recruits the tyrosine phosphatases SHP-1 and SHP-2 to the ITSM motif within its cytoplasmic tail, leading to the dephosphorylation of effector molecules such as CD3 ζ , PKC θ and ZAP70 which are involved in the CD3 T-cell signaling cascade. The mechanism by which PD-1 down modulates T-cell responses is similar to, but distinct from that of CTLA-4 as both molecules regulate an overlapping set of signaling proteins. PD-1 was shown to be expressed on activated lymphocytes including peripheral CD4+ and CD8+ T-cells, B-cells, Tregs and Natural Killer cells. Expression has also been shown during thymic development on CD4-CD8- (double negative) T-cells as well as subsets of macrophages and dendritic cells. The ligands for PD-1 (PD-L1 and PD-L2) are constitutively expressed or can be induced in a variety of cell types, including non-hematopoietic tissues as well as in various tumors. Both ligands are type I transmembrane receptors containing both IgV- and IgC-like domains in the extracellular region and contain short cytoplasmic regions with no known signaling motifs. Binding of either PD-1 ligand to PD-1 inhibits T-cell activation triggered through the T-cell receptor. PD-L1 is expressed at low levels on various non-hematopoietic tissues, most notably on vascular endothelium, whereas PD-L2 protein is only detectably expressed on antigen-presenting cells found in lymphoid tissue or chronic inflammatory environments. PD-L2 is thought to control immune T-cell activation in lymphoid organs, whereas PD-L1 serves to dampen unwarranted T-cell function in peripheral tissues. Although healthy organs express little (if any) PD-L1, a variety

of cancers were demonstrated to express abundant levels of this T-cell inhibitor. PD-1 has been suggested to regulate tumor-specific T-cell expansion in subjects with melanoma (MEL). This suggests that the PD-1/PD-L1 pathway plays a critical role in tumor immune evasion and should be considered as an attractive target for therapeutic intervention.

Pembrolizumab is a potent and highly selective humanized monoclonal antibody (mAb) of the IgG4/kappa isotype designed to directly block the interaction between PD-1 and its ligands, PD-L1 and PD-L2. Keytruda™ (pembrolizumab) has recently been approved in the United States for the treatment of patients with unresectable or metastatic melanoma and disease progression following ipilimumab and, if BRAF V600 mutation positive, a BRAF inhibitor.

